## 6. STUDY INTERVENTION

### 6.1. Study Intervention Administration

#### 6.1.1. Study Intervention Description

The HTD1801 drug substance, berberine ursodeoxycholate, is the salt formed between BBR and UDCA with a stoichiometry of 1:1. The HTD1801 drug product is a film coated tablet containing 250 mg of berberine ursodeoxycholate.

#### 6.1.2. Dosing and Administration

HTD1801 tablets (1000 mg dose) are administered twice daily (BID) with food. Subjects are instructed to take the entire contents of 1 pouch of study drug each morning and each evening with water and food (e.g., meal or snack). Each pouch will contain 4 identical white tablets. Subjects should retain the empty pouches and return them to the investigational site at the Week 6 study visit and Week 12 or Early Termination visit should it occur, along with any unused study drug. Returned unused study drug must not be re dispensed to subjects.

#### 6.1.3. Dose Modification

In the event of gastrointestinal (GI) discomfort as outlined in Section 9.3.8 at the starting dose of 1000 mg BID (4 tablets in the morning after a meal and 4 tablets in the evening after a meal), dose reduction is allowed per the following guidelines:

- For GI symptoms that are difficult for the subject to tolerate, decrease dose to 1500 mg per day (3 tablets in the morning after a meal and 3 tablets in the evening after a meal) for 1 week. If symptoms improve, subject should stay on that dose and not attempt to go back up to full dose.
- If symptoms persist after 1 week at the lower 1500 mg per day dose, decrease dose to 1000 mg per day (2 tablets in the morning after a meal and 2 tablets in the evening after a meal) for 1 week. If symptoms improve, subject should stay on that dose and not attempt to go back up to full dose.
- If symptoms persist after 1 week at the lower 1000 mg per day dose and are intolerable for the subject at this point, study drug is to be discontinued but the subject should continue to be followed as per the Schedule of Activities.

Subjects who will have their dose of study drug decreased will be monitored closely with serum ALP, aminotransferases and bilirubin levels being measured every 2 to 4 weeks. Elevations in ALP or bilirubin will be promptly recognized by the site PI and by the medical monitor because this is an open label study. If ALP levels after having been lowered on initial treatment go back up to baseline or higher on two subsequent occasions (baseline being the average of the historical value and the value at screening),, the subject will be deemed to be a treatment failure and will discontinue investigational study drug (see Section 7.3).

## **6.2. Preparation/Handling/Storage/Accountability**

### **6.2.1. Acquisition and Accountability**

HTD1801 250 mg tablets will be supplied by HighTide to each investigational site. The Investigator will be fully responsible for the security, accessibility, and storage of the study drugs while they are at the investigational site. The Investigator is also responsible for the education of site staff in the correct administration of the study drugs and must ensure that appropriate study drug accountability records are maintained.

The PI and study personnel are responsible for ensuring full investigational product accountability.

### **6.2.2. Formulation, Appearance, Packaging, and Labeling**

The HTD1801 drug product is a white to off-white film-coated tablet containing 250 mg of HTD1801.

Inactive excipients include a silicified microcrystalline cellulose (SMCC90), sodium carboxymethyl starch, and magnesium stearate. The tablets are coated with Opadry® immediate release film (product grade: 03A18375), resulting in an average gain of 15 mg/tablet. The qualities of all excipients are consistent with both the Chinese and US Pharmacopeia standards.

HTD1801 tablets are packaged into polyethylene terephthalate/aluminum foil/polyethylene (PET/AL/PE) pouches. Each pouch will contain 4 HTD1801 250 mg tablets and be affixed with a single-panel label that will describe the following information at a minimum: study drug, dose, kit number, Sponsor name, instructions for storage between 36°F and 46°F (2°C and 8°C), and includes the statements “Caution: New Drug - Limited by United States law to investigational use” and “Keep out of reach of children.”

An adequate supply of pouches will be placed into kits packaged for weekly use, and each subject will receive the appropriate number of kits to provide enough supplies until the Week 6 study visit to the investigational site. Each kit will bear a label describing the following information at a minimum: kit number, Sponsor name, instructions for storage between 36°F and 46°F (2°C and 8°C), and includes the statements “Caution: New Drug - Limited by United States law to investigational use” and “Keep out of reach of children.”

### **6.2.3. Product Storage and Stability**

HTD1801 tablets should be stored at 2-8°C in the original container and protected from moisture and light.

## **6.3. Study Intervention Compliance**

At applicable clinical visits during the study, subjects will be queried about their compliance with taking their assigned study drug as instructed. The number of full and empty study drug pouches will be captured on the eCRF.

## **6.4. Concomitant Therapy**

### **6.4.1. Permitted Concomitant Medications**

The use of permitted concomitant medications may continue during the study at the same dosage strength and frequency.

For subject taking cholestyramine or other bile acid sequestrant for pruritus, must be on a stable dose no more than once a day for at least 8 weeks prior to Baseline visit. Must be willing and able to take cholestyramine at least 2 hours before or after study medication.

### **6.4.2. Prohibited Concomitant Medications**

#### **6.4.2.1. Prohibited medications that are active against PBC**

Use of the following medications, active against PBC, will be prohibited during the study from Baseline through 28 days after completion:

UDCA

Obeticholic acid

Bezafibrate

Fenofibrate

It is important to emphasize that subjects will be counseled before starting investigational drug and at each visit not to take both UDCA and/or berberine together with HTD1801, as HTD1801 contains both UDCA and berberine.

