#### **4.4. End of Study Definition**

A participant is considered to have completed the study if he or she has completed all phases of the study including the last visit or the last scheduled procedure shown in the Schedule of Activities, Section 1.3.

The end of the study is defined as the date of completion of the last visit or procedure shown in the Schedule of Activities in the trial globally for the last subject in the study.

The end of enrollment if less than 30 subjects will be a collaborative decision between regulatory and Sponsor entities.

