### 7.3. Participant Discontinuation/Withdrawal from the Study

Subjects may be discontinued from the study for any of the following reasons:

- Noncompliance
  - Failure to receive study medication or treatment
  - Failure to comply with protocol requirements
  - Unauthorized, subject-initiated changes in dosing regimen
- Withdrawal of consent
  - Any subject who withdraws consent for any reason at any time during the study will be discontinued from the study, and the reason(s) will be documented on the appropriate eCRF page.
- Lost to Follow-Up

- For subjects who cannot be contacted for either a return for a scheduled clinic visit or for follow-up assessments as described, and who may be considered “lost to follow-up,” at least 3 documented attempts should be made to establish contact with and to instruct the subject on how to complete study procedures. In the final attempt to contact the subject, a letter should be sent by certified mail to the subject’s last known address
- Adverse Events
  - Study drug will be discontinued in an individual subject if the subject experiences a grade 3 and above adverse event (AE) for which the causality is considered as related to investigational study drug
- Treatment Failure
  - If any subject fails treatment after having their dose of HTD1801 reduced, their participation in the study will be ended and they will be allowed to resume their pre-study treatment for PBC. A subject will be deemed to have failed treatment if serum ALP, after having been lowered on initial treatment, returns to baseline or higher on two subsequent occasions (baseline being the average of the historical value and the value at screening).

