### **8.2. Screening (Days -28 to -1)**

Screening procedures must be completed within 28 days prior to the Baseline visit and can be performed across multiple days during this period. Screening clinical laboratory tests may be repeated once during Screening if the Investigator believes the results to be erroneous. In the event that Screening tests are repeated, the most current results will be used to determine eligibility. If screening procedures are completed and subject eligibility is confirmed, the full 28-day screening period may not be necessary.

During Screening, the following procedures must be conducted and assessments obtained. The information will be collected in the investigational site's standard source documents or in source document templates provided by the Sponsor.

- Informed consent if not obtained at pre-screening visit
- Confirm eligibility criteria
- Demographic information
- Medical history
- Assign subject ID # if not obtained at pre-screening visit
- Complete physical examination
- Vital signs
- Weight, height
- Electrocardiogram, 12 lead (ECG)

- Serum chemistry panel including GGT, Lipid panel — fasting, unsweetened clear coffee, tea or water permitted but no food after supper the evening before
- Complete blood count (CBC) with differential (no smear)
- INR
- Fibrinogen
- CRP
- Haptoglobin
- ELF
- G6PD
- IgM
- IgG
- AMA
- ANA
- TSH
- FSH (if needed to confirm menopausal status)
- Pruritus VAS
- Prior and concomitant medications

Subjects will be instructed to stop all prohibited medications (see Section 6.4) prior to beginning Baseline procedures. In particular, subjects will be cautioned against the use of UDCA until their participation in this study is complete.

NOTE: If the screening ALP value is more than  $\geq 30\%$  lower than the historical value obtained as part of standard of care, the subject will not qualify for enrollment but may be re-screened as soon as 4 weeks later. If on re-screening the ALP value continues to be  $> 30\%$  lower, the subject will not be included in the study.

### 8.3. Baseline/Day 0

Potential subjects who have successfully completed all of the Screening procedures and have met all the eligibility criteria (see Sections 5.1 and 5.2) will be eligible for enrollment in the study. Subjects will undergo the following Baseline procedures and assessments prior to the first dose of study drug:

- Confirmation of continued eligibility
- Update of medical history information

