#### **9.3.8.2. Treatment Failure due to HTD1801 Dose Reduction**

If any subject with PBC fails treatment after having their dose reduced, their study participation will be terminated and the subject would be able to resume their pre-study treatment for PBC after early termination study-required assessments completed. A subject will be considered to have failed treatment if the serum ALP, after having been lowered on treatment, returns to baseline or higher on two subsequent assessments (baseline is calculated as the average of the historical value and the value at screening).

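### The ban on PBC therapy has no defined end, contradicts the rule for treatment failures, and leaves subjects who stop for GI intolerance with no stated time to resume therapy

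*Protocol*

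**What the plan says.** **The ban.** Protocol 6.4.2.1 says of UDCA, obeticholic acid (OCA), bezafibrate and fenofibrate: "Use of the following medications, active against PBC, will be prohibited during the study from Baseline through 28 days after completion". The word completion has no object. The drug-interaction ban in 6.4.2.3, by contrast, is tied to named periods, Screening through Follow-Up.

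**Completion.** Protocol 4.4 gives the only definition: "A participant is considered to have completed the study if he or she has completed all phases of the study including the last visit".

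**Instruction at screening.** Protocol 8.2 says "subjects will be cautioned against the use of UDCA until their participation in this study is complete".

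**Treatment failure after dose reduction.** Protocol 7.3 says "their participation in the study will be ended and they will be allowed to resume their pre-study treatment for PBC". Section 9.3.8.2 adds a condition: the subject is "able to resume their pre-study treatment for PBC after early termination study-required assessments completed". Section 7.1 sends these subjects to 7.2, whose list of reasons for stopping drug does not include treatment failure.

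**GI intolerance.** At the last step of the dose-reduction ladder, Protocol 6.1.3 says "study drug is to be discontinued but the subject should continue to be followed as per the Schedule of Activities".

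**Anyone who stops drug.** Protocol 7.2 calls for an ET visit when drug is stopped. Sections 7.2 and 8.9 ask subjects who terminate before Week 12 to return 28 days after last dose. Study discharge is listed at the ET visit, although a later visit is still requested.

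**SAP.** Section 2.5.1.1 limits the primary analysis to on-treatment Week 12 data. Sections 2.3.8.3 and 3.4.1.1 summarise the Week 12 to Week 16 difference in ALP, ALT, AST and GGT. Section 3.2.3 puts prohibited medications in a listing. No section deals with laboratory values taken after a PBC therapy is restarted.

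**The concern.** Every subject enters on UDCA (inclusion criterion 3), so pre-study treatment includes a drug banned by 6.4.2.1. A site that follows 7.3 and 9.3.8.2 for a treatment failure breaches 6.4.2.1 as written, and a site that follows 6.4.2.1 withholds what 7.3 and 9.3.8.2 allow.

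The subject stopped for GI intolerance has no rule at all. HTD1801 was that subject's only permitted source of UDCA, and it has been withdrawn. The reason 6.4.2.1 gives about UDCA, that it should not be taken together with HTD1801, does not cover the time after HTD1801 stops. Two subjects who both stop after dose reduction can therefore be told different things about standard therapy, depending on the label given to the stop.

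At stake is an unplanned and uneven time without PBC therapy, which bears on patient safety. A smaller matter is post-treatment laboratory summaries that pool subjects back on therapy with subjects on none.

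**Working it through.** **Inputs.** Week 12 is Day 84 and Week 16 is Day 112 (Schedule of Activities). The follow-up interval is 28 days after last dose (7.2, 8.8, 8.9). Each of the two steps of the GI ladder lasts one week (6.1.3). The analysis windows are in SAP Table 2.

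**1. The protocol's own figure.** Last dose on Day 84 + 28 = Day 112. This agrees with the stated Week 16 day.

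**2. Completer.** If completion means treatment, the ban ends on Day 84 + 28 = Day 112, in line with 8.2. If it means the study as defined in 4.4, it ends on Day 112 + 28 = Day 140, after the last scheduled visit. Day 140 is stated nowhere; it follows only from combining the two sections.

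**3. Treatment failure after dose reduction.** Under 7.3 and 9.3.8.2 the wait is 0 days once the ET assessments are done. Under 6.4.2.1 it is 28 days after last dose, or 28 + 28 = 56 days if the clock starts at the 28-day visit. Section 9.3.8.2 does not say whether the 28-day visit belongs to the ET assessments. If it does, resumption comes later than the ET visit.

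**4. GI stop.** The earliest stop is about Day 0 + 7 + 7 = Day 14, assuming the first reduction falls at about Day 0. The days barred after a stop on day s are:

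| Stop day s | ET route: last dose + 28 | ET route: 28-day visit + 28 | Full schedule: 112 − s | Full schedule: 140 − s |
|---|---|---|---|---|
| 14 | 28 | 56 | 98 | 126 |
| 28 | 28 | 56 | 84 | 112 |
| 42 | 28 | 56 | 70 | 98 |
| 56 | 28 | 56 | 56 | 84 |
| 70 | 28 | 56 | 42 | 70 |

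The Day 112 column comes from 6.1.3 read as visits to Week 16, with 8.2 ending the UDCA caution there. On the full schedule, a gap of at least 60 days needs a stop by Day 112 − 60 = Day 52, or by Day 140 − 60 = Day 80 on the longer reading.

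**5. Reach into the data.**
- Primary endpoint: subjects off treatment are removed (SAP 2.5.1.1), so a restart of UDCA cannot enter it.
- Week 12 to Week 16 difference: a Week 12 value must fall on Day 71 to 90 and no later than 1 day after last dose. A subject stopped before Day 70 has no such value. Only stops on about Day 70 to 83 give a pair that a restart could affect.
- Week 16 window: this takes off-treatment samples after Day 90. On the ET route, a sample 28 days after last dose exceeds Day 90 only if the last dose is after Day 90 − 28 = Day 62, on nominal timing. On the full schedule, the Day 112 sample of any GI stopper falls in the window.
- Completers are barred to at least Day 112 on every reading.

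**6. Scale.** Protocol 4.3 reports GI discontinuation in 12% of subjects at 1000 mg BID in the NASH study and none in the PSC study. 0.12 × 30 = 3.6, so roughly 0 to 4 of 30 subjects if either rate carried over.

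**The case against.** The strongest reply is that a natural reading removes most of the difficulty. The 28-day interval is elsewhere tied to last dose, so completion in 6.4.2.1 plausibly means treatment, which gives Day 112 and matches 8.2. Section 4.4 describes someone who finished all phases, so applying it to an early stopper is strained. The Schedule of Activities has its own ET column and a footnote asking for a return 28 days after last dose, so following the Schedule after a GI stop may mean only that. Sections 7.3 and 9.3.8.2 can be taken as a specific exception to a general rule.

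Much of this stands. It makes Day 140 and the 98- and 126-day gaps the less natural readings. It does not supply the missing exception in 6.4.2.1, define completion, or say when a GI-stopped subject may resume therapy.

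Four stronger inferences are tempting, and the documents do not support them:
- That treatment failures resume at once. Section 9.3.8.2 requires the ET assessments first.
- That 8.2 conflicts with 7.3. Section 7.3 ends participation, and the caution in 8.2 ends with participation.
- That GI-intolerant subjects are left untreated for months. This needs an early stop and the full-schedule reading; the ET route gives 28 or 56 days. Section 4.2 expects markers to worsen over time, but as the argument for having no control arm. It does not address a short interruption of UDCA.
- That the off-drug laboratory data are confounded as a whole. Step 5 of the working shows how narrow the exposure is.

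**Conclusion.** The inconsistency is real, and the sponsor should resolve it. Section 6.4.2.1 has no anchor and no exception, it contradicts 7.3 and 9.3.8.2 for treatment failures, and follow-up after a GI stop can be read in two ways with no stated time for resuming PBC therapy.

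A completer's ban differs by 28 days between readings (Day 112 or Day 140). For a stop at about Day 14, the bar is about 28 or 56 days on the ET route and about 98 or 126 days on the full-schedule route, against none after the ET assessments for a treatment failure. The longer figures assume the first dose reduction at about Day 0 and visits to Week 16; they shrink day for day with a later stop.

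The case rests mainly on consistent instructions to sites and on patient safety. The statistical effect is limited to a few subjects in the Week 16 off-treatment laboratory summaries and, for stops on about Day 70 to 83, the Week 12 to Week 16 difference.

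**What to change.** **Protocol.** Reconcile 4.4, 6.1.3, 6.4.2.1, 7.1, 7.2, 7.3, 8.2, 8.9 and 9.3.8.2 so that they agree on:
- one end of the prohibition, anchored to a named event such as a specified dose or visit, for each of three cases: completers, treatment failures after dose reduction, and other early discontinuations including GI stops;
- one follow-up route after a GI stop;
- whether the ET assessments in 9.3.8.2 include the 28-day visit.

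The choice of rule in each case is for the sponsor and investigators.

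**SAP.** In the Week 16 summaries and the Week 12 to Week 16 difference, flag or separate ALP, ALT, AST and GGT values taken after a PBC therapy was restarted, using the concomitant-medication dates already collected.

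**Cost.** A protocol clarification and one flag in existing summaries. No added visits, tests or subjects.

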#### **6.4.2.2. Prohibited medications for the treatment of AIH**

Use of medications for the treatment of AIH other than prednisone or azathioprine is prohibited (e.g., Mycophenolate). Stable use of immunosuppressives for other indications may be permitted (see above).

#### **6.4.2.3. Prohibited medications with potential for drug-drug interaction**

In addition, certain concomitant medications have been identified for exclusion from this proof-of-concept study and are not to be taken at any time during the entire study (i.e., from Screening through Follow-Up). These exclusions are primarily due to the potential drug interaction profile of the BBR component of HTD1801. [Table 2](#) lists medications known to be strong inhibitors of P-glycoprotein (P-gp), CYP3A4, and CYP2D6; strong inducers of CYP3A4, as well as P-gp substrates with a narrow therapeutic index, and that are prohibited from concomitant use during this study.

Supplements with potential for drug-drug interaction should be discussed with the medical monitor prior to enrolling a subject.

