**Table 2: Prohibited Medications with potential for drug-drug interaction****Single Agents:**

P-glycoprotein	CYP3A4		CYP2D6
Clarithromycin	Clarithromycin	Ritonavir	bupropion
Erythromycin	Telithromycin	Saquinavir	fluoxetine
Amiodarone	Troleandomycin	Telaprevir	fluvoxamine
Digitalis	Nefazodone	Tipranavir	paroxetine
Dronedarone	St. John's wort	chloramphenicol	Quinidine
Carvedilol	Itraconazole	Rifampin	Terbinafine
Propafenone	Ketoconazole	Cobicistat	
Quinidine	Posaconazole	grapefruit juice	
Ranolazine	Voriconazole	conivaptan	
Verapamil	Atazanavir	Diltiazem	
Sildenafil	Boceprevir	Idelalisib	
Itraconazole	Darunavir	enzalutamide	
Ketoconazole	Indinavir	Mitotane	
Ritonavir	Lopinavir	carbamazepine	
Saquinavir	Nelfinavir	Phenytoin	
Telaprevir			
Lapatinib			

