### **9.2.2. Adverse Events**

Adverse events will be collected from the time at which the potential subject signs the ICF. Subjects will be instructed to report all AEs during the study and will be assessed for the occurrence of AEs throughout the study until at least 30 days after discontinuing the study drug. General and non-leading questions such as "How are you feeling?" should be asked when assessing the occurrence of AEs. The definition, reporting, and recording requirements for AEs are described in Section 9.3.

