## **9.3. Adverse Events and Serious Adverse Events**

### **9.3.1. Definition of Adverse Event (AE)**

The following definition of an AE will be used for this study: Adverse event means any untoward medical occurrence associated with the use of a drug in humans, whether or not considered drug related.

An AE can be any unfavorable and unintended sign (including an abnormal laboratory finding), symptom, or disease (new or exacerbated) temporally associated with the use of the investigational product, regardless of whether it is considered to be related to the investigational product.

The following are examples of AEs:

- Significant or unexpected worsening or exacerbation of the indication under study.
- Exacerbation of a chronic or intermittent preexisting condition, including an increase in frequency or intensity of the condition.
- New conditions detected or diagnosed after investigational product administration, even if they were present before the start of the study.
- Signs, symptoms, or the clinical sequelae of a suspected interaction with another medical product.
- Signs, symptoms, or the clinical sequelae of a suspected overdose of either investigational product or a concurrent medication.

Overdose should not be reported as an AE or serious adverse event (SAE), but rather the symptoms resulting from the overdose should be reported as such.

Examples of AEs do not include the following:

- Medical or surgical procedures (e.g., endoscopy, appendectomy). The medical condition that led to the procedure as the AE should be reported.
- Situations that are unwanted by the subject but in which an untoward medical occurrence did not occur, for example social inconvenience after admission to a hospital.
- Anticipated day-to-day fluctuations of a pre-existing disease or condition (present or detected before enrollment) that does not worsen overall.

- Expected progression of the disease being studied, including signs or symptoms of the disease, unless progression is more severe than expected for the subject's condition.

Adverse events may include post-treatment events that occur as a result of protocol-mandated procedures (e.g., invasive procedures, modification of the subject's previous therapeutic regimen).

Adverse events should be captured even if they occur during periods without drug treatment, post-treatment periods, known placebo treatment, or in a reference or control group receiving drug or nondrug therapy.

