### 9.3.4. Time Period and Frequency for Event Assessment and Follow-Up

AEs will be recorded starting after Screening and at every visit through the Week 16 Follow-Up Visit.

After the initial AE or SAE report, the investigator is required to proactively follow each subject and provide further information to the sponsor about the subject's condition. All AEs and SAEs will be followed until the occurrence of one of the following:

- The condition resolves.
- The AE or SAE is not related.
- The subject is lost to follow-up.
- The subject is followed for 30 days after the End-of-Study Visit (or other appropriate time frame).
- The subject starts another investigational product.

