### 9.3.6. Serious Adverse Event Reporting

1. Any SAE occurring after the subject signs the ICF and the study drug has been administered, as described in Section 9.3.2, must be reported to the Sponsor's or designee's pharmacovigilance department by phone, fax, or e-mail within 24 hours of the time the Investigator becomes aware of the SAE (Table 6). Any SAE reported by phone should be immediately followed up with the submission of the completed SAE report form. Urgent reporting of SAEs is required for the following reasons:
  - a. To enable the Sponsor to fulfill the reporting requirements to the appropriate regulatory authority
  - b. To facilitate discussion between the Sponsor and the Investigator about appropriate follow-up measures (if necessary)
  - c. To facilitate the Sponsor's rapid dissemination of information about AEs to other investigators or sites in a multicenter study
  - d. To facilitate reporting unanticipated problems involving risk to subjects to the institutional review board (IRB) or independent ethics committee (IEC).

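### A serious event caused by stopping a Table 2 drug before first dose has no 24-hour reporting requirement, and that stop needs no medical-monitor discussion

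*Protocol*

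**What the plan says.** **The ban and the stop.** Protocol 6.4.2.3 says the drugs in Table 2 ("Prohibited Medications with potential for drug-drug interaction") "are not to be taken at any time during the entire study (i.e., from Screening through Follow-Up". Section 8.2, which describes Screening, gives the working instruction: "Subjects will be instructed to stop all prohibited medications (see Section 6.4) prior to beginning Baseline procedures". Table 2 is part of Section 6.4, so the instruction covers it. None of the numbered exclusions in 5.2 names Table 2 drugs. Exclusion 22 leaves unsuitable prior therapy to the investigator's opinion.

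**Who is consulted.** Section 6.4.2.3 adds: "Supplements with potential for drug-drug interaction should be discussed with the medical monitor prior to enrolling a subject". Exclusion 17 separately requires medical-monitor approval for chronic immunosuppressives. Nothing comparable is stated for a prescription drug in Table 2.

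**Reporting.** Section 9.3.6 attaches the 24-hour rule to "Any SAE occurring after the subject signs the ICF and the study drug has been administered".

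**When AE capture starts.** Section 9.2.2: "Adverse events will be collected from the time at which the potential subject signs the ICF". Section 9.3.4: "AEs will be recorded starting after Screening and at every visit through the Week 16 Follow-Up Visit". Table 1 first marks adverse event monitoring at Baseline, and the list of Screening procedures in 8.2 does not include it.

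**The concern.** The protocol itself asks for the medication change. Table 2 includes drugs often taken long term, such as amiodarone, digitalis, carbamazepine, phenytoin and paroxetine. For a supplement the site must speak to the medical monitor before enrolling. For one of these drugs it need not.

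If stopping the drug led to a serious event before first dose, the event would follow from a study instruction to a consented subject. Section 9.3.6 gives as reasons for urgent reporting that the sponsor can discuss follow-up measures with the investigator and inform other sites quickly. Both reasons apply equally to such an event, yet the rule as worded does not reach it. What is at stake is how promptly the sponsor learns of the event, and whether anyone beyond the enrolling investigator considers the stop beforehand. This is a subject-safety matter and has no bearing on the efficacy analysis.

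**Working it through.** There is no plan figure to reproduce and no power or error-rate calculation applies. The check is a reading of the sections side by side, with one subtraction.

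**Step 1: does the protocol direct a stop after consent?** Consent comes before any study-specific Screening evaluation (13.1, Table 1). The instruction in 8.2 is given during Screening and covers all of Section 6.4. So the direction falls after consent and before Day 0.

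**Step 2: how long can the interval be?** Screening runs from Day -28 to Day -1 (8.2, Table 1), and the first dose is on Day 0.
- Earliest stop: 0 - (-28) = 28 days before first dose.
- Stop on the last Screening day: 0 - (-1) = 1 day before first dose.

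The interval is therefore up to 28 days within one screening period. Consent may be given earlier, at optional pre-screening, but the stop instruction belongs to Screening, so 28 days is the relevant bound. Sections 6.4.2.3 (from Screening) and 8.2 (before Baseline procedures) give different start points, and the protocol does not say which prevails.

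**Step 3: does the 24-hour rule apply in that interval?** The rule in 9.3.6 has two conditions joined by *and*.

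| Time of SAE | Consent signed | Study drug given | 24-hour rule applies |
|---|---|---|---|
| After the stop, before the Day 0 dose | Yes | No | No |
| After the Day 0 dose | Yes | Yes | Yes |

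**Step 4: is the event captured at all?** Yes. Section 9.2.2 collects AEs from consent. Section 9.3.1 has the investigator note AEs mentioned at Screening and Baseline, and says AEs should be captured in periods without drug treatment. Section 9.3.2 calls for detailed SAE reports and medical-monitor review, with no dosing condition but also no time limit. The gap is the clock, not the capture.

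**Step 5: do the AE start points agree?**

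| Place | Start |
|---|---|
| Protocol 9.2.2 | Consent |
| Protocol 9.3.4 | After Screening |
| Protocol Table 1 | Baseline visit |

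They do not. SAP 2.3.8.1 repeats the 9.3.4 start.

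**Step 6: what pre-enrolment medical-monitor involvement is stated?** For supplements, a discussion (6.4.2.3). For immunosuppressives, approval (exclusion 17). For prescription drugs in Table 2, none.

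**The case against.** **Table 2 users may not be candidates at all.** Section 6.4.2.3 describes these drugs as identified for exclusion and applies the ban from Screening. On that reading a user is simply not enrolled, and the sentence in 8.2 is a generic one that goes on to single out UDCA. This has some force. However, no numbered exclusion bars a Table 2 user, and 8.2 says in terms that subjects will be told to stop everything in Section 6.4. A site following 8.2 as written would give the instruction.

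**Exclusion 22 already protects.** A candidate who needs a Table 2 drug cannot comply with 6.4.2.3, and an investigator should exclude that person. Prior and concomitant medications are recorded at Screening. This protection is real but partial: it rests on one investigator's judgement and requires no discussion with the medical monitor or the prescriber.

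**Pre-dose SAEs are not lost.** This stands in full. A reader might infer that such an event would go unrecorded or never reach the sponsor. Sections 9.2.2, 9.3.1 and 9.3.2 do not support that. Section 9.3.5 also refers to a study procedures manual with further SAE guidance. That manual is not among the documents, so it may already deal with pre-dose events.

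**Table 6 shows 24 hours without conditions.** Read alone, it would cover any SAE. But it sits inside 9.3.6 and is cited by the sentence that carries the dosing condition, so it does not clearly widen the rule.

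**Section 9.3.1 is weak support.** It refers to events that "occur as a result of protocol-mandated procedures (e.g., invasive procedures, modification of the subject's previous therapeutic regimen", but the sentence concerns post-treatment events. It shows that the protocol recognises a changed regimen as a possible cause of harm. It does not settle how a pre-dose event is handled, and the point does not depend on it.

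**Conclusion.** The point holds as a limited safety-wording matter, worth considering in the next amendment. As written, a serious event caused by a protocol-directed stop before first dose is collected but carries no 24-hour requirement, for an interval of up to 28 days. The AE start point is stated in three different ways. The medical-monitor discussion that applies to supplements does not extend to prescription drugs in Table 2.

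This rests on three assumptions: that 8.2 means what it says for Table 2 drugs, that the two conditions in 9.3.6 are both required, and that the study procedures manual does not already close the gap.

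Two stronger readings should be resisted. One is that this will affect many subjects: the documents give no count of Table 2 users and report no such event, and the make-up of the drug list says nothing about how many of the up to 30 subjects take anything on it. The other is that the protocol must set a fixed stop-to-dose interval for each drug: the documents contain no data from which to choose one. Nothing here affects the sample size, the primary test or its interpretation.

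**What to change.** (a) In 9.3.6, add a sentence such as: *SAEs between consent and first dose that may be due to a protocol-mandated procedure, including stopping a prior medication, are reported within 24 hours.* Align 9.3.4 and Table 1 with the start at consent in 9.2.2, and carry the same start into SAP 2.3.8.1.

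(b) In 6.4.2.3, extend the existing medical-monitor discussion to any prescription Table 2 drug a candidate is taking at Screening. Require it before the drug is stopped, and state that a candidate who needs the drug is not enrolled.

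The cost is a few lines of text, amendment approval under 13.5, slightly more safety reporting, and one added discussion for each affected candidate. No new visit or test is needed.
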